5.1.4 Treatment Compliance

Study subjects should be counseled on the need to meet 100% compliance with study drug. Investigator or designee should ensure that study subjects meet this goal throughout the study

period. Compliance will be verified by the accounting of each study drug at each monthly visit starting with the Baseline (Visit 2).

If compliance during the tamsulosin hydrochloride run-in period is less than 80% or greater than 120% of study medication the subject is considered non-compliant and will be excluded from the study.

If compliance for blinded treatment is less than 80%, the Investigator or designee is to counsel the subject and ensure steps are taken to improve compliance. Subjects who are less than 80% compliant with the dosage regimen for any two consecutive visit periods during the study should be withdrawn from the study.

5.2 Demographics and Baseline Characteristics

5.2.1 Demographics

The subject's date of birth (or age, if local regulations do not allow recording of subject's date of birth), gender, race, ethnicity, height, and weight will be recorded at Screening/tamsulosin hydrochloride run-in (Visit 1).

5.2.2 Medical History

Medical history (other than for overactive bladder), including smoking history will be obtained at Screening/tamsulosin hydrochloride run-in (Visit 1) from each subject. All relevant past and present conditions, as well as prior surgical procedures will be recorded for the main body systems.

5.2.3 Diagnosis of the Target Disease, Severity, and Duration of Disease

A detailed history of OAB and lower urinary tract symptoms (LUTS) due to Benign Prostatic Hyperplasia (BPH) for each subject will be obtained at Screening/tamsulosin hydrochloride run-in (Visit 1). This includes date of onset of OAB symptoms, OAB symptoms at time of diagnosis and at Screening, OAB non-drug therapy and medication history for OAB and reason for treatment termination. In addition information regarding the history of BPH and LUTS will be collected.

5.3 Efficacy Assessment

5.3.1 Patient Diary – Micturition and Incontinence

During the study, subjects will be requested to complete a "3-day diary" which will be implemented on an electronic handheld device. This diary will collect data on micturition and incontinence, sleep interruption, protective garments, vital sign measurements and the Patient Perception of Intensity of Urgency Scale (PPIUS) prior to Visits 2, 3, 4, and 5. The information from the diaries will be used to evaluate the efficacy of treatment. Therefore, subjects will receive full instructions and training on how to complete the diary at Screening/tamsulosin hydrochloride run-in (Visit 1) and will be counseled on the importance of completing the diaries prior to the next visit. The diaries and questionnaires will be reviewed during each visit after Screening/tamsulosin hydrochloride run-in (Visit 1) by the Investigator or designee to ensure accuracy of completion.

A training diary will be completed in the first 2 weeks of the tamsulosin hydrochloride run-in period. The purpose of this training diary is to familiarize the subject with using the electronic handheld device and for the Investigator to assess the ability and willingness of the subject to complete the diary. During these 2 weeks the Investigator will remotely evaluate diary completion and will provide additional instructions if necessary. During this evaluation period at least one telephone contact will take place with the subject. The diary that is completed during the last 3 days before randomization will be used to establish Baseline data. Therefore, it is very important to ensure that any compliance or completion issues are discussed during the 2-week training diary.

Diaries will be completed at home for 3 consecutive days prior to each visit: Baseline (Visit 2), Week 4 (Visit 3), Week 8 (Visit 4), and Week 12/End of Treatment (Visit 5). Site staff will contact the subject approximately 7 days prior to the scheduled visit to remind the subject they need to complete the electronic diary, review completion instructions and review changes to concomitant medications and adverse events (if applicable).

A diary day starts at midnight and ends at midnight the following day. Time to bed with intention to sleep, time to wake with intention of staying awake, type of episode (urination/incontinence), time of episode, urgency severity (see Section 5.3.2), measure of urine volume voided, and sleep interruption will be recorded by the subject in the micturition diary.

At Baseline (Visit 2), diary data, including frequency of micturition (urination episodes) and urgency episodes (grade 3 and 4) with or without incontinence will be reviewed to confirm inclusion criteria.

Voiding episodes will be recorded in one of three ways: “urination”, “incontinence”, or “both” in the electronic diary. Micturitions will be counted for “urination” episodes in which the subject fully voids in the toilet. “Incontinence” will be counted for episodes in which the full void was incontinent and the subject did not make it to the toilet to finish urinating. If a subject experienced incontinence and then passed urine into the toilet this should be recorded as “both”. During analysis, “both” will be counted towards micturition and incontinence. In addition to micturition information, the electronic diary will also collect time of medication intake and vital signs along with sleep interruption and protective garment use (see Table 1 Schedule of Assessments).

5.3.2 Patient Perception of Intensity of Urgency Scale (PPIUS)

The Patient Perception of Intensity of Urgency Scale (PPIUS) will be completed as part of the micturition diary.

For each micturition and/or incontinence episode, subjects will be asked to rate the degree of associated urgency according to the following validated 5-point scale. The categories are recommended by the Committee for Proprietary Medicinal Products [CPMP/EWP/18/01, Final].

- 0 – No, urgency, I felt no need to empty my bladder, but did so for other reasons.
- 1 – Mild urgency, I could postpone voiding as long as necessary, without fear of wetting myself.
- 2 – Moderate urgency, I could postpone voiding for a short while, without fear of wetting myself.
- 3 – Severe urgency, I could not postpone voiding, but had to rush to the toilet in order not to wet myself.
- 4 – Urge incontinence, I leaked before arriving at the toilet.

The PPIUS will be completed at Baseline (Visit 2), Week 4 (Visit 3), Week 8 (Visit 4), and Week 12/End of Treatment (Visit 5).

5.3.3 Total Urgency and Frequency Score (TUFS)

The Total Urgency and Frequency Score (TUFS) is calculated by adding the PPIUS scores of every void in a patient's 3-day diary, and dividing this by the number of days recorded in the diary [Chapple et al, 2014].

5.3.4 International Prostate Symptom Score (IPSS)

The International Prostate Symptom Score (IPSS) consists of seven questions concerning urinary symptoms and one question concerning quality of life.

The IPSS will be completed at Screening (Visit 1), Baseline (Visit 2), Week 4 (Visit 3), Week 8 (Visit 4), and Week 12/End of Treatment (Visit 5).

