Safety analyses will be done on the Safety Analysis Set (SAF), which consists of subjects who received at least one dose of double-blind medication. Treatment emergent adverse events will be coded using the MedDRA dictionary and will be summarized by treatment group. The number and percentage of treatment-emergent AEs, SAEs, AEs leading to discontinuation, and AEs related to study drug will be summarized by system organ class, preferred term and treatment group. Laboratory variables (biochemistry, hematology, and urinalysis) will be descriptively summarized for Baseline (Visit 2), Week 4, Week 8, and Week 12/End of Treatment and change from Screening to End of Treatment will be summarized by treatment group. Vital sign changes will be summarized by treatment group. Categorical changes in vital signs will also be examined. In addition, post-void residual volumes as measured by bladder sonography and Q_{max} will be summarized by change from baseline. Centrally assessed ECGs will also be summarized by treatment group.

Interim analyses:

Not applicable.

V. FLOW CHART AND SCHEDULE OF ASSESSMENTS

Flow Chart

mirabegron 25 mg QD plus tamsulosin hydrochloride 0.4 mg QD	mirabegron 50 mg QD plus tamsulosin hydrochloride 0.4 mg QD
placebo matched to mirabegron 25 mg QD plus tamsulosin hydrochloride 0.4 mg QD	placebo matched to mirabegron 50 mg plus tamsulosin hydrochloride 0.4 mg QD

[figure not shown]

Table 1 Schedule of Assessments

	Screening/ Tamsulosin Hydrochloride Run- In	Treatment Period				Follow-up Phone Call
		2	3	4	5	
Visit	1	2	3	4	5	6
Day	-28	1	28	56	84	114
Week	-4	0	4	8	12	16
Visit Windows	+/- 3 d	—	+/- 7 d	+/- 7 d	+/- 7 d	+/- 3 d
Visit Windows (Study Days) ^a	-31 to -25	—	21 to 35	49 to 63	77 to 91	111-117
Informed Consent	X					
Inclusion/Exclusion Criteria	X	X				
Medical History and OAB History	X					
Demographics	X					
Enter 4-week tamsulosin hydrochloride run-in ^b	X					
Reminder Phone Call ^c		X	X	X	X	
Randomization ^d		X				
Physical Exam	X				X	
Weight and Height	X					
Office Visit Vital Signs (pulse and blood pressure)	X	X	X	X	X	
Serum PSA	X					
Serum chemistry, hematology & urinalysis ^{e, f}	X	X	X	X	X	
12-Lead ECG ^g	X	X	X	X	X	
PVR (Ultrasonography or Bladder Scan)	X	X	X	X	X	
Uroflowmetry (Q _{max}) ^h	X				X	
IPSS	X	X	X	X	X	
Medication History and OAB Medication History ⁱ	X					
Concomitant Medications Assessment	X	X	X	X	X	X
Adverse Event Assessment ^j	X	X	X	X	X	X
Dispense Study Drug	X	X	X	X		
Drug Accountability		X	X	X	X	

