3.2 Inclusion Criteria

Inclusion Criteria assessed at Visit 1 (Screening).

Subject is eligible for the study if all of the following apply:

1. Institutional Review Board (IRB)/Independent Ethics Committee (IEC)-approved written Informed Consent and privacy language as per national regulations (e.g., HIPAA Authorization for US sites) must be obtained from the subject or legally authorized representative prior to any study-related procedures (including withdrawal of prohibited medication, if applicable).
2. Men ≥ 40 years of age with history of OAB symptoms (urinary frequency and urgency with or without incontinence) while taking tamsulosin hydrochloride 0.4 mg daily for at least 2 months to treat LUTS due to BPH.

3. Subject has symptoms of OAB (frequency of ≥ 8 micturitions per day and urgency episodes of ≥ 2 per day) for ≥ 3 months prior to Screening.
4. Subject has an IPSS score ≥ 8 .
5. Subject has Prostate-Specific Antigen (PSA) < 4 ng/mL OR PSA ≥ 4 but < 10 ng/mL with a prostate biopsy that is negative for cancer in the past two years.
6. Subject is willing and able to complete the 3-day diary (including urine volumes, vital sign measurements), and Quality of Life questionnaires.
7. Subject and their spouses/partners who are of childbearing potential must be using a highly effective method of birth control, which includes established use of oral, injected or implanted hormonal methods of contraception, placement of an IUD or IUS. Birth control must be practiced from Screening and continue throughout the study and for 30 days after the final study drug administration. In addition, sperm donation will not be allowed throughout the study and for 30 days after the final study drug administration.
8. Subject agrees not to participate in another interventional study while on treatment.

Inclusion Criteria assessed at Visit 2 (Baseline) based on the 3-day diary:

9. Subject continues to meet all inclusion criteria of Visit 1 (Screening).
10. Subject must experience an average of 8 or more micturitions per day over the 3-day diary period.
11. Subject must experience an average of 2 or more episodes of urgency per day (grade 3 or 4) over the 3-day diary period.

Waivers to the inclusion criteria will **NOT** be allowed.

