5.4.6 Electrocardiogram (ECG)

A single 12-lead ECG will be recorded at Screening/tamsulosin hydrochloride run-in (Visit 1), Baseline (Visit 2), Week 4 (Visit 3), Week 8 (Visit 4), and End of Treatment (Visit 5). ECG will be taken with the subject in the supine position (subject is allowed to be sitting if unable to be supine).

ECGs will be submitted to a central laboratory to allow for central reading (ECG recordings will be performed according to ICH guidelines E14 to make them readable and interpretable for potential later assessment by an independent cardiologist). Recordings will be made at a speed of 25 mm/s and all leads have to include at least four complexes. This is according to the standard setting on the machines.

The ECGs should be transmitted from the machine to the central laboratory (following the steps indicated in the user manual). In addition, one print copy of the original ECG traces should be maintained in the study file. These should be clearly marked with the subject identification number (in such a way that they are anonymized), visit date, and visit number, and should be kept with the source documents.

The ECG machine will produce automatically calculated interval duration measurements and an evaluation on the printed ECG. The manually read analysis reports of the central ECG readings will be made available to the Investigators (within 72 hours). The final ECG reports sent by the central laboratory must be reviewed by the Investigator and should be used for immediate safety assessment and subject care since there might be slight changes from the initial analysis produced by the ECG machines.

If the QTcF interval is >450 ms on the printed ECG at Visit 2, an expedited central ECG reading (within 24 hours) should be requested. In this case the final ECG report should be received/reviewed before the subject is allowed to be randomized.

The ECG report itself should not be captured on the eCRF, but will be captured in the central ECG laboratory database. Only the visit, ECG date, automated QTc, overall ECG interpretation and relevant comments will be captured in the eCRF.

If specific concerns regarding the cardiac safety of a subject exist, a dual approach is recommended:

- On-site evaluation of the ECGs should be conducted by a local cardiologist,

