7 STATISTICAL METHODOLOGY

The statistical analysis will be coordinated by the responsible biostatistician of Astellas. A Statistical Analysis Plan (SAP) will be written to provide details of the analysis, along with specifications for tables, listings and figures to be produced. The SAP will be finalized before database softlock at the latest. Any deviations from the analysis planned in SAP will be justified in the Clinical Study Report (CSR).

Prior to Database Lock, a Final Review of Data and TLFs Meeting will be held to allow a review of the clinical trial data and to verify the data that will be used for analysis set classification. If required, consequences for the statistical analysis will be discussed and documented. A meeting to determine analysis set classifications may also be held prior to database hard lock.

In general, baseline is defined as the last measurement before the first dose of double-blind study drug. For variables based on the electronic diary, the 3 days of the diary recorded prior to Visit 2/Baseline (Week 0) will be used to derive these variables at baseline just as the 3 diary days before each post-baseline visit will be used to derive these variables at these visits.

The End of Treatment (EOT) visit is defined as the last post-baseline visit during the double-blind study period for which data is available. The EOT visit value for diary variables is the average or number of the diary measurements for Week 12, as applicable. If no Week 12 diary data measurements are available, then the last available earlier post-baseline average or number of the diary measurements within a designated visit window will be used (LOCF). Data from the EOT visit will be analyzed to account for subjects prematurely terminating the study and is regarded as the primary visit. The EOT visit will be Week 12/EOT (Visit 5) for subjects who complete the study.

All statistical comparisons will be made using a two-sided test at $\alpha = 0.05$ significance level and confidence intervals (CIs) will be reported with a coverage consistent with this significance level unless specified otherwise.

All efficacy and safety variables will be summarized using descriptive statistics. Continuous variables will be summarized using the descriptive statistics number of non-missing observations (N), mean, standard deviation (SD) or standard error (SE), minimum, median, and maximum unless specified otherwise. Categorical variables will be described using N and percent.

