7.4.2 Analysis of Secondary Endpoints

Secondary variables are change to end of treatment in mean incontinence episodes per day, mean volume voided per micturition, mean number of urgency episodes (grade 3 and 4) per day, IPSS total score and subscales (Voiding, Storage, and Quality of Life), Symptom Bother and Total Health related quality of life scores as assessed by OAB-q questionnaire (and subscales), TUFS, PPBC, EQ-5D-5L, and TS-VAS.

An analysis of change from baseline in PRO values using a Mixed Model Repeated Measures (MMRM) with geographic region, age group, time (visit), and a time-by-treatment interaction as factors and PRO value at baseline as a covariate will serve as a sensitivity analysis. The repeated measures model will present LS means and two-sided 95% CIs for changes from baseline within each treatment group.

Analysis of mean change in number of incontinence episodes per day from Baseline to End of Treatment will be performed on the FAS-I using ANCOVA model, p-values will be calculated by stratified ranking ANCOVA. The response variable is standardized ranks on change from Baseline to End of Treatment, with Baseline standardized ranks as covariates and geographic region as a stratum. Standardized ranks are used to adjust for differences in the number of subjects at each geographic region. Further details may be found in the Statistical Analysis Plan.

The number of incontinence episodes and protective garment use during the 3-day diary period will be analyzed using a mixed effects Poisson regression model with treatment group, age group, and geographic region as factors and number of incontinence episodes at baseline as a covariate. Differences in LS means between mirabegron and placebo will be calculated together with 95% CI.

Other secondary efficacy variables will be analyzed using the same ANCOVA model as described for micturitions (refer to Section [7.4.1.1](#)). Descriptive analyses of the EQ-5D-5L will be in the Clinical Study Report. Other planned utility indices and analyses will be calculated in a separate report from the Statistical Analysis Plan and Clinical Study Report.

Responder analyses will be performed for 50% reduction in micturition frequency and for number of subjects with less than 8 micturitions per day at End of Treatment.

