7.5.3 Vital Signs

Pulse rate, systolic blood pressure, and diastolic blood pressure will be summarized by treatment group using descriptive statistics (mean, standard deviation, minimum, maximum and median) for baseline value, post-baseline time point values (Week 4, Week 8, and Week 12/EOT), and change from baseline to each post-baseline time points. The average change from baseline to end of treatment for each vital sign variable will be analyzed using the ANCOVA model with treatment group and geographic region as fixed factors and baseline vital sign value as covariate. Results will be summarized separately for office based measurements and HBPM. No p-values will be calculated.

An analysis of change from baseline of vital signs using a Mixed Model Repeated Measures (MMRM) model with geographic region, age group, time (visit), and a time-by-treatment interaction as factors and the baseline values as covariate will serve as another sensitivity analysis. The repeated measures model will present LS means and two-sided 95% CIs for changes from baseline within each treatment group.

Number and percentage of subjects with more than 2/5/10/15/20 mmHg increase from baseline in SBP, more than 2/5/10/15 mmHg increase in DBP or more than 5/10/15 bpm increase from baseline in pulse rate, on 2 consecutive post-baseline visits will be summarized by treatment group. Number and percentage of subjects with vital sign values shifting between JNC-7 defined risk categories will be summarized by treatment group. These categories are listed below:

Category	Systolic BP (mm Hg)	Diastolic BP (mm Hg)
Normal	< 120	<80
Prehypertension	120-139	80-89
Hypertension Stage 1	140-159	90-99
Hypertension Stage 2	\geq 160	\geq 100

Number and percentage of subjects with a PR > 100 bpm at any office visit or by HBPM will be summarized by treatment group separately.

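### IPSS and office blood pressure and pulse are measured twice before randomization, but their models adjust only for the Visit 2 value, so some precision already collected goes unused

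*Protocol*

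**What the plan says.** **Two measurements.** Section 5.3.4 states: "The IPSS will be completed at Screening (Visit 1), Baseline (Visit 2), Week 4 (Visit 3", and continues to the later visits. In Table 1 the row "Office Visit Vital Signs (pulse and blood pressure" is marked at Visits 1 to 5.

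**Same nominal background.** Inclusion criterion 2 (3.2) takes men with OAB symptoms "while taking tamsulosin hydrochloride 0.4 mg daily for at least 2 months" before Visit 1. The run-in in 2.2.1 continues 0.4 mg once daily for four weeks to Visit 2.

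**One baseline.** Section 7 says that, in general, "baseline is defined as the last measurement before the first dose of double-blind study drug". For IPSS and office vital signs that is Visit 2.

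**Models with that one value.** For IPSS, 7.4.2 says: "Other secondary efficacy variables will be analyzed using the same ANCOVA model as described for micturitions". That model (7.4.1.1) has treatment, region and age group as factors and baseline as covariate. The 7.4.2 MMRM for patient-reported outcomes also uses one baseline value. For vital signs, 7.5.3 specifies ANCOVA with "treatment group and geographic region as fixed factors and baseline vital sign value as covariate", plus an MMRM with the baseline value as covariate. Office and home measurements are summarized separately, and 7.5.3 plans no p-values.

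For IPSS and office vital signs, the Protocol gives the Visit 1 value no role in these models.

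**The concern.** A single IPSS score or office reading carries visit-to-visit noise. A second pre-randomization reading on the same dose normally adds information about a man's underlying level, and so about his outcome. If the model omits it, the interval for the mirabegron-placebo difference can be wider than the collected data require.

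IPSS is a listed secondary endpoint. Safety and tolerability is the secondary objective, and blood pressure and pulse are named under adverse events of special interest (5.4.3.2). Section 1.3.1 reports mean shifts of only about 1 mmHg and 1 bpm with mirabegron 50 mg. With no p-values planned for vital signs, interval width matters to how such shifts are read.

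The Protocol leaves detail to the SAP, which was not available here, but it fixes the baseline rule and the covariates itself.

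**Working it through.** **1. The plan's own figure.** The Protocol gives no power or precision figure for IPSS or vital signs, only the primary sample size. With difference 0.65, SD 2.7, two-sided alpha 0.05 and 80% power:

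n per arm = 2 × (1.960 + 0.842)² × 2.7² / 0.65² ≈ 271, against 272 stated. Power at 272 per arm is 80.2%. Then 544/0.85 = 640 and 640/0.65 = 984.6, so 985. All of this reproduces and is not at issue.

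**2. Inputs for the check.** Let r2 be the correlation of Visit 2 with the outcome, r1 that of Visit 1 with the outcome, and r12 that between Visits 1 and 2. None is in the Protocol; all are assumed.

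**3. Formulas (outcome variance set to 1).**
- Visit 2 only: residual variance = 1 − r2².
- Both covariates: residual variance = 1 − (r1² + r2² − 2·r1·r2·r12)/(1 − r12²).
- Proportional fall = (r1 − r2·r12)² / [(1 − r2²)(1 − r12²)].

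The last line is never negative. It is zero only when r1 = r2·r12, that is, when Visit 1 adds nothing once Visit 2 is known.

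**4. Results, with r2 = r12 = r.**

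| r | Visit 2 only | r1 = r | r1 = 0.9r | r1 = 0.8r |
|---|---|---|---|---|
| 0.5 | 0.750 | 0.667 (−11.1%) | 0.697 (−7.1%) | 0.720 (−4.0%) |
| 0.6 | 0.640 | 0.550 (−14.1%) | 0.589 (−7.9%) | 0.618 (−3.5%) |
| 0.7 | 0.510 | 0.424 (−17.0%) | 0.472 (−7.5%) | 0.500 (−1.9%) |
| 0.8 | 0.360 | 0.289 (−19.8%) | 0.342 (−4.9%) | 0.360 (0%) |

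Interval width changes with the square root of the variance:
- r1 = r, r from 0.5 to 0.7: 1 − √0.889 = 5.7% to 1 − √0.830 = 8.9% narrower.
- r1 = 0.9r: about 2.5% to 4.0% narrower.
- r1 = 0.8r: 0% to 2.0% narrower.

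**5. Other decay patterns.** With r12 = 0.70 and r2 = 0.60, the fall is 5.2% at r1 = 0.55, 2.0% at r1 = 0.50 and 0% at r1 = 0.42 (first-order autoregressive decay, 0.70 × 0.60).

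**6. Selection at entry.** IPSS must be 8 or more, and pulse outside 60 to 90 bpm excludes. This truncates the readings and weakens the correlations. Simulation with equal correlations of 0.5 to 0.7 and assumed mean/SD of 18/6 (IPSS) and 72/10 (pulse) gave falls of 9.6-15.5% for IPSS and 7.1-12.8% for pulse. The equal-correlation gain shrinks but does not vanish.

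**The case against.** The strongest reply is that nothing in the Protocol is wrong. A last-pre-dose baseline used as an ANCOVA covariate is valid and consistent, and the Protocol leaves further detail to the SAP. That stands: this is an improvement, not a defect.

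The size is also open. Visit 1 is about 16 weeks before Week 12 and Visit 2 about 12, so the older value may well predict less, and a gain of zero is within range. Before Visit 1 the men used their own tamsulosin with adherence unmeasured, whereas the run-in uses supplied drug with an 80-120% compliance rule. The dose is the same, but the two readings are not strict replicates. That also stands, and it is why a range is given.

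For blood pressure and pulse, section 5.4.2 collects home readings in triplicate, morning and evening, for 3 days before each visit from Visit 2 on: up to 3 × 2 × 3 = 18 per visit. The home analysis therefore already has an averaged baseline. The point is limited to the separate office analysis.

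Two wider readings are tempting:
- **ECG.** A reader might infer that the Visit 1 and Visit 2 ECGs should be averaged for QTcF change. ECG has no covariate model in 7.5.5, and averaging lacks the protection of a second covariate. With r12 = 0.70, r2 = 0.60 and r1 = 0.42, change-score variance is 2(1 − 0.60) = 0.80 from Visit 2 but 1 + 0.85 − 1.02 = 0.83 from the mean. It could also leave QTcF on a different baseline from the other ECG measures.
- **Primary endpoint.** A reader might infer the same loss there, since "A training diary will be completed in the first 2 weeks of the tamsulosin hydrochloride run-in period". Section 5.3.1 presents that diary as device familiarization and a check of ability and willingness. Its number of recorded days and its completeness are not stated, and the primary baseline is already a 3-day diary mean.

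**Conclusion.** The point holds as a minor efficiency improvement for IPSS and for office blood pressure and pulse. Residual variance would fall by about 11-17% if Visit 1 predicts as well as Visit 2 (correlations 0.5 to 0.7). Over correlations of 0.5 to 0.8, it would fall by about 5-8% if Visit 1 correlates 10% less with the outcome, and by 0-4% if 20% less. The upper range should not be read as the expected gain, because the Protocol gives no correlation and some decay is plausible.

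A reader might also infer that the planned analyses are biased or invalid. The documents do not support that: adjusting for Visit 2 alone gives a valid comparison, only a somewhat less precise one.

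**What to change.** In the IPSS models (the 7.4.1.1 ANCOVA as applied by 7.4.2, and the 7.4.2 MMRM) and in the office blood pressure and pulse models (7.5.3 ANCOVA and MMRM), add the Visit 1 value as a second covariate beside the Visit 2 baseline. Keep change scores measured from Visit 2, so that endpoint definitions and the Visit 2-based hypertension criteria in 5.4.1 and Appendix 4 are untouched. Fill a missing Visit 1 value with the overall mean across both arms. Few should be missing, because entry criteria rest on these measures.

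A second covariate is preferable to averaging the two visits. It absorbs any mean shift between them and asymptotically cannot lose precision, whereas a simple average can.

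The cost is a sentence in 7.4.2 and 7.5.3, or in the SAP, settled before unblinding, and one degree of freedom per model. With 544 men analysed, that is roughly 1/544, or 0.2%, of variance if Visit 1 proves uninformative. No new data, visits or patients are needed, and a covariate measured before randomization cannot bias the comparison.
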